### **2.3 Exploratory Pre-specified Outcomes**

1. The individual components of the primary outcome.
2. To assess the effect of *CYP2C19*\*17 on bleeding risk and MACE.
3. The effect of *CYP2C19*\*2 or \*3 genotype on multiple recurrent MACE events in the individual subject.
4. To compare the occurrence of MACE in patients with reduced function *CYP2C19* allele(s) receiving clopidogrel to those with wild type (WT) genotype receiving clopidogrel.
5. To compare the occurrence of MACE in patients with reduced function *CYP2C19* allele(s) receiving ticagrelor to those with WT genotype receiving clopidogrel.
6. To assess the effect of coronary artery disease (CAD) presentation: a) Stable coronary artery disease b) Unstable angina or non-ST elevation myocardial infarction (NSTEMI), and c) ST-elevation myocardial infarction (STEMI) on the effectiveness of ticagrelor in patients with reduced function *CYP2C19* allele(s) and on the association of *CYP2C19* genotype and occurrence of MACE.

7. To assess the mechanism of coronary stent thrombosis in patients with reduced function *CYP2C19* allele(s) receiving ticagrelor versus clopidogrel.
8. To compare MACE and bleeding outcomes in all patients randomized to the conventional therapy arm versus the prospective genotyping arm.
9. To assess implementation of a CLIA-approved *CYP2C19* pharmacogenetic testing on the Spartan® platform (accuracy of genetic testing by sequence analysis and genotype failure rates).
10. To assess compliance with dual anti-platelet therapy by phone survey.
11. Performing a pharmacoeconomic analysis of the conventional therapy approach as compared with the genotype based approach in subjects who undergo PCI.
12. To assess patients' attitudes towards genotyping and the results of genotyping by survey.

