### 15.2.2 Revised Sample Size Calculations

At the time of this protocol revision (Version 8), the estimated event rate for the primary endpoint across all LOF subjects is 4.8%, substantially lower than the assumptions made in Section 15.2.1. We propose performing updated power calculations using a revised minimum detectable effect of a hazard ratio of 0.50. This effect size is justified by several arguments. First, ticagrelor has already been shown to reduce MACE events by about 16% in all ACS patients, regardless of genotype, in the PLATO trial. However, because our study treatment represents a precision medicine, pharmacogenomic approach, we expect a much greater treatment effect in the targeted LOF population. Second, such effect sizes have been seen in other studies involving CYP2C19 \*2 and \*3 alleles(2,40). Third, a meta-regression analysis of studies comparing event rates in (primarily) clopidogrel-treated patients who were LOF vs. WT suggested an inverse relationship between the overall event rate and the WT vs. LOF advantage, such that the predicted HR

in very low event rates was consistent with 0.50. Finally, at low event rates, a large effect must exist within the LOF population in order to achieve reasonable number-needed-to- treat (NNT) values, since the genotype-guided dual antiplatelet treatment is expected to have no effect in the WT population. For example, if the event rate is 4% in LOF subjects on clopidogrel, and 2% in LOF subjects on ticagrelor, that 50% reduction would equate to a NNT of 50 subjects within the LOF sub-population. If the prevalence of LOF alleles is 30% in the overall population, that would equate to an NNT of 167. Under initial assumptions, the NNT in the LOF sub-population would have been 25 subjects, equating to an overall NNT of 75. Thus, from the perspective of NNT, we are powered to detect a smaller effect than under initial assumptions.

Additional assumptions play a role in the power calculations. First, we assume that around the total enrollment mark of 3900 subjects, 20% of subjects enrolled from

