## 15.5 Specification of the Primary Analyses

Hypothesis 1A. The effect of genotype-guided antiplatelet therapy versus conventional care in patients with a reduced function *CYP2C19* allele will be estimated using a Cox proportional hazards regression model, with covariates including variables used for stratified randomization and other subject factors associated with MACE. The analysis will be conducted under the intention-to-treat principle, with follow-up beginning at randomization, but with genotype defined by the Taqman genotyping assay. Those whose prospectively defined genotype disagrees with their TaqMan-based genotype will nevertheless be analyzed based on the TaqMan result, which is the only result that is available in both arms. A sensitivity analysis will be done, taking into account the Spartan result. In the retrospective genotyping group, reduced function status will be determined by the TaqMan assay results at least one year after PCI. Subjects who withdraw or are lost during follow-up will be treated as censored at the date of last contact. Patients who complete follow-up at 12 months will be considered censored from that point onward. The proportional hazards assumption will be assessed visually using plots of scaled Schoenfeld residuals. A two-sided likelihood ratio test will be used to assess the significance of the partial effect of treatment; a p-value less than 0.05 will be considered statistically significant. Kaplan- Meier curves will be used to display survival free of MACE estimates over the first year of follow-up.

Hypothesis 1B. It is also important to determine the effect of genotype-guided antiplatelet therapy versus conventional care in patients with the wild type *CYP2C19* allele. In this case, both groups will be given clopidogrel, but the genotype-guided group patients and their physicians will know prospectively that they have the wild-type allele, at least based on the Spartan platform. The analysis will be done as outlined above in the LOF group, again defined by the TaqMan-based assessment of wild-type status. It is expected that the null hypothesis will prevail, but it is important to confirm that knowledge of genotype in and of itself does not have an effect on the rate of MACE events.

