Finally, note that the entire allocation of type 1 error is placed on Hypothesis 1A, and the analysis of Hypothesis 1B is seen as confirmatory of the null hypothesis. If the null hypothesis in 1A is rejected, i.e. a treatment benefit is seen with ticagrelor versus clopidogrel in LOF patients (or the converse), then (and only then) a formal test of Hypothesis 1B will be conducted at the 0.05 level. The purpose of this second test is to inform the overall assessment of treatment effect in the entire randomized study population. In any case, an assessment of treatment effect in the overall randomized study population will be done for estimation and descriptive purposes only, since it will have insufficient power to detect a treatment effect. If the null hypothesis in 1B is rejected, then that result will be factored into any overall assessment of benefit of the prospective genotyping treatment strategy.

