where  $S(\cdot)$  is the overall underlying survival curve for freedom from events,  $t$  is time in years. Note that if the subject experiences the primary endpoint, the value of  $t$  is not tied to the event time itself, but rather reflects the visit date (roughly 1 month, 6 months, or one year) representing the effective amount of follow-up for that patient (time from randomization to last follow-up date). To calculate  $S(\cdot)$ , we simply use the Kaplan-Meier curve for the entire study population. This fraction therefore represents the fraction of a “risk year” to which that subject was exposed, i.e. it is an estimate of the proportion of events occurring within a year that have occurred at the follow-up time for the specific individual. Note that we consider  $w(t)$  to be a fixed quantity, rather than a parameter, though technically it is estimated from the entire data set.

We further assume that the event rates (1-year probabilities) are:

$$\lambda_{WT,CL} = \lambda_1$$

$$\lambda_{LOF,TIC} = \lambda_2$$

$$\lambda_{LOF,CL} = \lambda_3$$

We also assume that the rate of wild type subjects exposed to clopidogrel ( $\lambda_1$ ) is the same whether they are in the conventional therapy or the prospective genotyping group. This is a fundamental assumption, but one which will also be ultimately tested.

The treatment effect of interest can be expressed as  $\lambda_2/\lambda_3$ , that is, the relative risk associated with

ticagrelor in LOF subjects. The trial's primary hypothesis is that this number is substantially less than 1.0. (Relative risk reduction is 1 minus this quantity). Finally, let  $\alpha$  be the population prevalence of the LOF genotype in the population being randomized. We can now define the likelihood contributions of members of each of the three groups of "incomplete" subjects.

For those in the PG-WT and PG-LOF groups, the likelihood contributions, respectively, are:

$$L(\lambda_1|X, t) = [\lambda_1 * w(t)]^X * [1 - \lambda_1 * w(t)]^{(1-X)}$$

$$L(\lambda_2|X, t) = [\lambda_2 * w(t)]^X * [1 - \lambda_2 * w(t)]^{(1-X)}$$

For those in the CT group, the likelihood contribution is a weighted average of the likelihood contributions that would be obtained under (WT, CLOP) and (LOF, CLOP) conditions, weighted by the probability of each genotype, namely:

$$L(\lambda_1, \lambda_3, \alpha|X, t) = (1 - \alpha) * L_1(X, t) + \alpha * L_3(X, t)$$

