where  $L_1$  and  $L_3$  have the obvious definitions parallel to the 'known-genotype' likelihoods spelled out above. If this were the only data available, then the 4 parameters ( $\lambda_1, \lambda_2, \lambda_3, \alpha$ ) would not be identifiable, i.e.  $\alpha$  and  $\lambda_3$  would be completely confounded. However, we have one further piece of data: the numbers of LOF and WT subjects in the PG group. These numbers can be put into a binomial likelihood with  $\alpha$  as the only parameter. The random variable corresponding to this proportion is statistically independent (at least uncorrelated), with all the other likelihood pieces. Therefore, the overall likelihood is the product of all the conditional likelihood pieces for the members of the 3 groups, along with this binomial likelihood for the prevalence of LOF. This serves to identify both  $\alpha$  and therefore  $\lambda_3$  as parameters. Thus in this complete likelihood, all 4 parameters are identified. Thus, the *incomplete* data provides a likelihood that *is* informative about the treatment effect (subject to the null hypothesis assumption regarding the effect of knowledge of genotype on the WT/CLOP response). The likelihood from these data can be combined with the simple TaqMan binomial data to derive a combined likelihood which incorporates both pieces of information.

*Estimation of Information Time:* We can also estimate the proportion of total study information contained in the current data. First, we estimate the expected information at the end of the trial as the

inverse of the expected square of the standard error of the hazard ratio of interest. Our expected power of 85.8% implies that our expected z-score at the end of the trial is 3.031. Given a minimum detectable effect size of 0.50, the expected standard error at study end is 0.2287 ( $\log(0.5)/3.031$ ). Thus the expected final information is 19.1. Second, the available information in the current data is calculated using a profile likelihood approach to estimate the standard error of the current estimate of the treatment effect. The ratio of the current information to the expected final information is the estimated information time.

*Calculation of conditional power:* Conditional power is a function of the current effect estimate z-score and information time. Its formula is:

$$CP(t, Z_t) = 1 - \Phi\left[\frac{\Phi^{-1}(0.975) - Z_t \sqrt{t}}{\sqrt{(1-t)}}\right] - (\Phi^{-1}(0.975) + \Phi^{-1}(P_0)) * \sqrt{(1-t)}$$

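### Hypothesis 1B is presented as confirming no effect of genotype knowledge in wild-type patients, but its only decision rule is a 0.05 difference test, whose non-rejection cannot show that

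*Combined protocol and SAP*

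**What the plan says.** Section 2.1 words Hypothesis 1B as a null claim: in wild-type patients on clopidogrel, knowing the genotype leaves MACE risk unaltered. It is tested formally only if the 1A null is rejected.

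Section 15.5 repeats the 1A method in patients who are wild type by TaqMan: a Cox model with a two-sided likelihood ratio test. It expects the null to stand and adds that "it is important to confirm that knowledge of genotype in and of itself does not have an effect on the rate of MACE events". It then says that "the analysis of Hypothesis 1B is seen as confirmatory of the null hypothesis". The formal test is at 0.05. A consequence is stated for rejection of 1B; none is stated for non-rejection. The analysis of the whole randomized population "will be done for estimation and descriptive purposes only, since it will have insufficient power to detect a treatment effect", and section 2.3 lists that comparison among the exploratory outcomes.

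The documents contain no margin, no interval criterion, no wild-type event rate and no power figure for 1B. All the MACE power tables in section 15.2 concern carriers of a reduced function allele (LOF).

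On the 1A threshold, section 15.5 uses p < 0.05. Section 15.8 (efficacy monitoring) sets the final test at 0.0495, with critical value 1.965, after up to three looks at 3.291. The conditional-power formula in Appendix C uses the 0.975 normal quantile, which is 1.96.

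**The concern.** A difference test can reject equality. Failing to reject leaves open every effect inside the confidence interval. Section 15.5 gives the test the task of supporting the null, expects non-rejection, and does not say how to read it. If the interval is wide, a report that follows the plan's wording would claim something the data cannot carry, namely that the genotyping strategy is neutral in the roughly 64% of patients who are wild type. Any statement about the strategy in all patients combines the carrier effect with the wild-type effect, so the error would pass into it.

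The 1A threshold is a smaller matter. A final p-value between about 0.0494 and 0.05 would be significant by one section and not by another, and that result also decides whether 1B is formally tested.

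**Working it through.** **The plan's own figures first.** Freedman's formula at HR 0.50 with 80% power gives 71 events. At the 4.5% overall rate this is 71/0.045 = 1,578 LOF subjects, against 1,560 in Table 4. The same method gives 85.7% power at n = 5,270, against 85.8% stated. The 1A design figures are not in dispute.

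**Wild-type patients at n = 5,270.** Table 4 has 1,275 Korean patients among 4,467, and section 15.2.2 assumes a 20% Korean share of further enrolment. (Its 85% column agrees: 138 of the next 688 are Korean.)
- Korea: 1,275 + 0.20 × 803 = 1,436. North America: 5,270 − 1,436 = 3,834.
- LOF prevalence is 59% and 28%, so wild type = 1,436 × 0.41 + 3,834 × 0.72 = 3,349, or 64% of 5,270.
- After 5% loss: 3,349 × 0.95 = 3,182.

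**Event rate (assumed).** I take 3.0% to 4.8%. The upper end is the rate that section 15.2.2 reports across all LOF subjects. The lower end is a judgement.

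**Interval at an observed HR of 1.0.** SE(log HR) = 2/√events; limits = exp(±1.96 × SE).

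| Wild-type rate | Events | SE | 95% CI |
|---|---|---|---|
| 3.0% | 95.5 | 0.205 | 0.67–1.49 |
| 3.5% | 111.4 | 0.190 | 0.69–1.45 |
| 4.0% | 127.3 | 0.177 | 0.71–1.42 |
| 4.8% | 152.7 | 0.162 | 0.73–1.37 |

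**Chance of missing a true HR of 1.25.** The conventional arm has d1 = 1,591 × rate and the guided arm d2 = 1.25 × d1. SE = √(1/d1 + 1/d2), and the miss probability is about 1 − Φ(0.223/SE − 1.96).
- 3.0%: d1 = 47.7, d2 = 59.7, SE = 0.194, z = 1.15, missed 79%.
- 4.8%: d1 = 76.4, d2 = 95.5, SE = 0.154, z = 1.45, missed 69%.
- For a true HR of 0.75 the same method gives 74% and 62%.

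The conclusion does not hang on the low rate. At the 10.5% baseline rate of section 15.2.1, d1 = 167, d2 = 209, SE = 0.104 and z = 2.15, so a true HR of 1.25 would still be missed about 42% of the time.

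**Could an interval rule succeed?** For a 95% CI centred on 1.0 to fit inside 0.80–1.25 (an illustrative margin; the plan has none), the trial needs 4 × (1.96/ln 1.25)² = 309 events, about two to three times the 95–153 expected.

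**1A threshold.** With looks at 40%, 60% and 80% of information at 3.291, the multivariate normal calculation gives:

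| Final critical value | Overall two-sided alpha |
|---|---|
| 1.96 | 0.05045 |
| 1.9643 (p = 0.0495) | 0.04995 |
| 1.965 (p ≈ 0.0494) | 0.04987 |

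At the expected z of 3.031 in Appendix C, power is 85.79% with 1.96 and 85.68% with 1.965. Two details follow. The pair printed in section 15.8 (0.0495 and 1.965) is not quite one threshold. And the 3.031 is itself 1.96 + 1.071, so Appendix C carries the unadjusted value in two places.

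**The case against.** The strongest reply is that this is loose wording and not a faulty decision rule. Section 15.5 introduces 1B as determining the effect in wild-type patients, plans a Cox estimate, places all type I error on 1A, and says the 1B test is there to inform the overall assessment. That is fair. A reader might infer that the plan licenses an equivalence claim from a non-significant 1B; it does not, because nothing is attached to non-rejection. What stands is that the same section, and the hypothesis in section 2.1, state the purpose as confirming the null, and no sentence tells the analyst otherwise. The one sentence on confidence intervals, in section 15.6, covers binomial measures only.

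A reader might also infer that an untested premise undermines the primary result. Appendix C says of equal wild-type rates in the two arms: "This is a fundamental assumption, but one which will also be ultimately tested". It makes the interim likelihood for incomplete data "subject to the null hypothesis assumption regarding the effect of knowledge of genotype on the WT/CLOP response". But that likelihood serves interim monitoring, where data with TaqMan results dilute the dependence, and the final 1A analysis does not use it. The number-needed-to-treat passage in section 15.2.2, where "the genotype-guided dual antiplatelet treatment is expected to have no effect in the WT population", is a design illustration. Rewording section 15.5 would change neither, so neither carries this point.

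On the threshold, it can be said that section 15.8 already governs the final look. It does in intent, but section 15.5 and Appendix C have not been brought into line.

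**Conclusion.** The point holds as one of wording and reporting. Sections 2.1 and 15.5 give 1B a confirmatory role that a two-sided 0.05 difference test cannot fill. With about 95–153 wild-type events, even a hazard ratio of exactly 1.0 would leave increases of 37–49% and reductions of 27–33% inside the 95% interval.

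These figures rest on an assumed wild-type rate of 3.0–4.8%, the enrolment mix and prevalences of section 15.2.2, and 5% loss. The principle rests on none of them. The documents do not support the stronger readings that 1A is compromised or that an equivalence test is obligatory.

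The 1A threshold conflict is real and tiny: about 0.0006 in overall alpha and 0.1 point of power. It should not be read as material type I error inflation. The 0.05 for 1A in section 2.1 is consistent with section 15.8 if read as the overall type I error rate.

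**What to change.** **For 1B**
- In section 2.1, reword 1B as estimating the difference in MACE between arms in wild-type patients and, if 1A is rejected, testing for one.
- In section 15.5, remove the two statements that the analysis confirms the null, and state that non-rejection is not evidence of no effect.
- Report the wild-type hazard ratio with its 95% confidence interval whatever 1A shows, beside the overall-population hazard ratio and its interval. Base any strategy-level statement on those intervals.
- Claim no meaningful effect only if a margin was fixed before database lock and the interval lies inside it. If no such claim is wanted, no margin is needed.

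**For 1A**
- Choose one final threshold: critical value 1.965 (p about 0.0494), or p < 0.0495 (critical value 1.9643). Use it in sections 15.5 and 15.8 and in the conditional-power formula of Appendix C. The 0.05 for 1A in section 2.1 can stay.

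**Cost.** Text changes only; no patients or data. The downside is that the wild-type result will probably have to be reported as inconclusive. The 1A edit matters only for a p-value in the narrow gap below 0.05, where it would decide significance and whether 1B is formally tested.

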## 15.6 Specification of the Secondary Analyses

For secondary analyses involving 1-year endpoints (e.g. MACE, bleeding), Cox proportional hazards models with appropriate covariates will be used to compare the 1-year rate of secondary endpoints according to intention-to-treat classification. A p-value less than 0.05 will be considered statistically significant. Additionally, unadjusted treatment effects will also be estimated and tested as a secondary analysis. Confidence intervals for binomial measures will be computed using the Wilson CI method for 95% coverage probability. Mechanisms of stent failure for subjects with coronary stent thrombosis and with reduced function *CYP2C19* allele will be compared between ticagrelor and clopidogrel using Pearson's chi-squared test.

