#### **4. PRELIMINARY STUDIES**

Mega explored the effect of *CYP2C19* reduced function allele in a separate cohort of 1,477 subjects with acute coronary syndromes who were treated with clopidogrel in the TRITON-TIMI 38. The pharmacogenetic cohort receiving clopidogrel represented approximately 10% of the total original study population. Among the clopidogrel-treated subjects there was a 12.1% composite event rate of death from cardiovascular causes, myocardial infarction, and stroke as compared with 8% of patients with WT *CYP2C19* genotype (i.e. relative 53% increased risk). The risk of stent thrombosis in the carriers was 2.6% as compared with 0.8% in the WT group.

Simon observed similar results in their analysis of 2,208 patients in the FAST-MI cohort. They observed a higher event rate in carriers of two *CYP2C19* reduced function alleles (21.5% vs. 13.3%, adjusted hazard ratio (HR), 1.98; 95% CI, 1.10-3.58). In patients undergoing PCI (n=1535), the adjusted risk of death, MI, or stroke was 3.58 times higher in patients with 2 *CYP2C19* reduced function alleles (95% CI, 1.76-7.51, p=0.005).

In a collaborative meta-analysis, with data extracted from 9 previous studies involving 9,685 study participants receiving clopidogrel (91.3% with PCI, 54.5% with ACS), carriers of 1 (HR, 1.55; 95% CI, 1.11-2.17) or 2 (HR, 1.76; 95% CI, 1.24 – 2.50, p=0.002) reduced function *CYP2C19* alleles had a significantly increased risk of composite end point (CV death, MI, or stroke). Furthermore, a significantly increased risk in stent thrombosis was observed with carriers of 1 (HR, 2.67; 95% CI, 1.69-4.22, p<.0001) or 2 (HR, 3.97; 95% CI, 1.75-9.02, p=.001) reduced function *CYP2C19* alleles. Similarly, a study by Hulot of 4,905 patients with PCI showed an odds ratio of 3.45 for stent thrombosis for individuals carrying a *CYP2C19*\*2 allele.

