### **Stent thrombosis**

Definite (presence of acute coronary syndrome with angiographic or autopsy evidence of thrombus or occlusion) or probable (unexplained deaths within 30 days after the procedure or acute myocardial infarction involving the target-vessel territory without angiographic confirmation).

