Based on data from Mega and Schuldiner, a hazard ratio as low as 0.60 for ticagrelor versus clopidogrel in reduced function allele carriers may be expected. We intend to power the study to detect a hazard ratio of 0.65 or smaller. This will

require a total of 1,694 patients with reduction function alleles to be randomized, and thus 5,270 patients will be enrolled.

**Table 3.** Required sample size for 80% power

	Minimum detectable effect, hazard ratio		
	0.60	0.65	0.70
Number with reduction function allele required	1,241	1,694	2,401
Number with reduced function to enroll assuming 5% drop out	1,307	1,784	2,528
Number with reduced function allele enrolled at South Korean sites	508	508	508
Number with reduced function allele to enroll at non-Korean sites	799	1,276	2,020
Total number enrolled at Korean sites, assuming 50% prevalence	1,015	1,015	1,015
Total number to enroll at non-Korean sites, assuming 30% prevalence	2,665	4,255	6,734
Total number enrolled	3,680	5,270	7,749

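### The stent-thrombosis mechanism test in 15.6 compares only patients who had a thrombosis, so it tests the mix of mechanisms among cases and not whether the drug changes the risk of any mechanism

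*Combined protocol and SAP*

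**What the plan says.** The aim is item 7 of section 2.3: "To assess the mechanism of coronary stent thrombosis in patients with reduced function" alleles, ticagrelor versus clopidogrel. Section 12.2 repeats it among the exploratory outcomes.

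Section 15.6 gives the method. The material analysed is "Mechanisms of stent failure for subjects with coronary stent thrombosis and with reduced function" alleles, and the mechanisms "will be compared between ticagrelor and clopidogrel using Pearson's chi-squared test". The same section says "A p-value less than 0.05 will be considered statistically significant". That sentence follows the description of the Cox models, and no different rule is given for the mechanism comparison.

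Two neighbouring provisions matter:

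- Item 1 of section 2.3 lists "The individual components of the primary outcome", and stent thrombosis is one of them. This analysis covers all carriers but is not split by mechanism.
- Section 12.3 defines stent thrombosis by certainty of diagnosis, beginning "Definite (presence of acute coronary syndrome with angiographic or autopsy evidence of thrombus or occlusion", and then a probable category. No mechanism categories are listed there or in 15.6.

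**The concern.** Being in the comparison depends on having had a thrombosis after randomization. Because treatment is expected to change who has one, the cases on ticagrelor and the cases on clopidogrel are not groups formed by randomization.

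The null hypothesis of the Pearson test is that the mechanism shares are equal among cases. That differs from the statement that the drug leaves the risk of each mechanism unchanged. The two separate most clearly when the drug acts on one mechanism only: the untouched mechanism becomes a larger share of a smaller total. A reader of the results table could take the shift as a drug effect on the mechanism that did not change. At stake is the interpretation of one exploratory result, and no trial decision rests on it.

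**Working it through.** **The plan's own figure.** The documents give no figure for the mechanism test. The denominator comes from section 15.2.1, where the trial will "require a total of 1,694 patients with reduction function alleles to be randomized, and thus 5,270 patients will be enrolled". Check, with HR 0.65, 12% control risk, two-sided 0.05 and 80% power:

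- Events = 4 × (1.960 + 0.842)² / (ln 0.65)² = 169.2, rounded up to 170.
- Ticagrelor risk = 1 − 0.88^0.65 = 7.97%; mean risk = (12% + 7.97%) / 2 = 9.99%.
- Patients = 170 / 0.0999 ≈ 1,703, within 0.5% of 1,694.
- At 1:1 allocation, 1,694 / 2 = 847 carriers per arm.

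**Other inputs.** The clopidogrel stent-thrombosis rate is varied from 0.8% to 2.6%. Section 4 supplies the ends of that range: "The risk of stent thrombosis in the carriers was 2.6% as compared with 0.8% in the WT group". These are background data and not planning values of this trial; 1.5% is an intermediate value. Assumptions not in the documents: two mechanisms, 75% of clopidogrel thromboses platelet-driven and 25% mechanical, with ticagrelor hazard ratios of 0.3 and 1.0 respectively.

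**Shift in the mix.** The mechanical share among ticagrelor cases is (0.25 × 1.0) / (0.25 × 1.0 + 0.75 × 0.3) = 0.25 / 0.475 = 53%, against 25% on clopidogrel. The thrombosis rate cancels, so this holds across the whole range. The mechanical risk is identical in the two arms.

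**Expected cases per arm** (847 × rate × share × hazard ratio):

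| Clopidogrel rate | Platelet-driven, clopidogrel vs ticagrelor | Mechanical, each arm |
|---|---|---|
| 0.8% | 5.1 vs 1.5 | 1.7 |
| 1.5% | 9.5 vs 2.9 | 3.2 |
| 2.6% | 16.5 vs 5.0 | 5.5 |

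**Power in that scenario** (simulated binomial counts, 20,000 to 40,000 replicates, two-sided 0.05):

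| Clopidogrel rate | Planned Pearson test among cases | Platelet-driven incidence, uncorrected two-proportion test | Platelet-driven incidence, Fisher's exact test |
|---|---|---|---|
| 0.8% | 14% | 27% | 14% |
| 1.5% | 23% | 47% | 38% |
| 2.6% | 35% | 74% | 65% |

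On the Fisher column, the one suited to counts this small, the gain is about 0, 14 to 15 and 30 points.

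**A single table.** Take 11 cases of mechanism A and 11 of B on clopidogrel, and 2 of A and 11 of B on ticagrelor. The Pearson test among cases gives p = 0.041, and B's share goes from 11/22 = 50% to 11/13 = 85%. Over all carriers, B occurs in 11/847 in each arm (p = 1.00). The whole difference lies in A, 11/847 against 2/847 (p = 0.012, uncorrected).

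**Uniform reduction.** If both mechanisms are halved, the shares do not move and the planned test rejects in about 4% to 5% of trials. A comparison of any stent thrombosis over all carriers rejects in roughly 16%, 32% and 50% at the three rates.

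**Size of the planned test.** With no drug effect on either mechanism, the Pearson test among cases rejects in about 4% to 5% of simulated trials at each of the three rates.

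**The case against.** The strongest reply is that the aim can be read as descriptive: when a stent thromboses, why did it? A table of cases answers that question. The documents nowhere say that the result will be read causally or as ticagrelor causing mechanical failures. This stands, and it limits the point. What remains is that 15.6 attaches a between-drug significance test to the table, with no descriptive label and no incidence beside it.

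Three stronger readings are tempting, and the documents or the arithmetic do not support them:

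- *The plan would miss a drug that reduces every mechanism.* The mechanism test would, but such an effect is a fall in stent thrombosis overall, and the pre-specified component analysis addresses that. Only the mechanism-selective case is left uncovered, because the components are not split.
- *The small expected counts make the chi-squared test invalid.* Many simulated tables do have an expected cell below 5, but no inflation of the type I error was found.
- *An incidence analysis would gain much power.* The larger gains (27%, 47% and 74% against 14%, 23% and 35%) rest on an uncorrected test. With Fisher's test the gain at 0.8% is nil. The lower rates may also be nearer to this trial: section 15.2.2 reports a 4.8% primary-endpoint rate across carriers, whereas the 2.6% comes from a cohort whose carriers had a 12.1% composite rate. Proportional scaling (an assumption) gives 2.6% × 4.8 / 12.1 = 1.0%.

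**Conclusion.** The point holds in a limited form. The planned comparison conditions on a post-randomization event and therefore speaks to case mix, not to the effect of the drug on the risk of any mechanism. That follows from the wording of 15.6 and needs no assumed rates. The illustrations do: the move from 25% to 53% rests on the assumed 75/25 split and hazard ratios of 0.3 and 1.0, and the power figures rest in addition on 847 carriers per arm and the 0.8% to 2.6% range.

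The case for change is interpretability more than power. Importance is low: the aim is exploratory, and Hypothesis 1A, the sample size, the error allocation and the bleeding endpoint are untouched.

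**What to change.** In section 15.6:

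- Define the mechanism categories in advance; no mechanism-specific analysis can be specified without them.
- For each category, report the count and 1-year cumulative incidence over all TaqMan-defined reduced-function patients by randomized arm. Give a cause-specific hazard ratio or a risk difference with its 95% confidence interval, using an exact method when events are few.
- Keep the table of mechanisms among cases, labelled as descriptive only.

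Beyond agreeing the categories, this costs a few lines of SAP text and code, with no additional patients or follow-up. The drawback is wide intervals for each mechanism, which reflect how little information the trial will hold on this question.
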